9.2.3 Exclusion criteria

Patients meeting any of the following exclusion criteria (see Annex 3: Additional information) will be excluded from the analysis:

• A verified ambulatory or primary/ secondary hospital discharge diagnosis of valvular atrial fibrillation in the baseline period;

- A verified ambulatory or primary/ secondary hospital discharge diagnosis indicating pregnancy in the baseline period;
- A verified ambulatory or primary/ secondary hospital discharge diagnosis of a transient cause of atrial fibrillation in the baseline period;
- A verified ambulatory or primary/ secondary hospital discharge diagnosis of venous thromboembolism (VTE) in the previous or same quarter of the index date;
- A claim for hip or knee replacement surgery in the 60 days prior to or on the index date;
- A prescription of heparin or fondaparinux in the 60 days prior to or on the index date;
- A prescription of more than one oral anticoagulant (rivaroxaban, apixaban, edoxaban or phenprocoumon) on the index date;
- A prescription of warfarin or dabigatran in the baseline period or on the index date;
- A verified ambulatory or primary/ secondary hospital discharge diagnosis of end-stage kidney disease or a claim for dialysis in the baseline period;
- Patients receiving an initial dose of rivaroxaban 10 mg/ 2.5 mg or edoxaban 15 mg (these dosages are not indicated for the treatment of NVAF).
- A prescription of contraindicated drug for apixaban or rivaroxaban due to drug interactions (i.e. azole antifungals and HIV protease inhibitors) in the 60 days before or on the index date.

For the main analysis, patients will be followed from the index date until the first diagnosis of the respective outcome event, discontinuation of the index drug, death, end of continuous insurance in the SHI or the end of the study period (31 December 2017), whichever comes first. Patients will be censored in all analyses if they switch to phenprocoumon or another NOAC (including dabigatran), receive a prescription of heparin/ fondaparinux, warfarin, rivaroxaban 10 mg/ 2.5 mg, edoxaban 15mg or a contraindicated drug as defined above. For specific analyses, the end of follow-up may differ as described in 9.3.1.

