9.3 Variables

9.3.1 Exposure definition

As exposure, we will assess prescriptions of phenprocoumon and NOACs, i.e. rivaroxaban (15 mg or 20 mg once daily), apixaban (2.5 mg or 5 mg twice daily), edoxaban (30 mg or 60 mg once daily). All prescriptions will be assessed based on the documented dispensation date. A detailed list of products with the corresponding central pharmaceutical number (CPN) of the study drugs is displayed in Annex 3: Additional information.

Each patient will be assigned to one of the four exposure groups based on the index drug: new users of phenprocoumon, rivaroxaban, apixaban or edoxaban.

Exposure time for phenprocoumon and NOACs starts on the index date and will be calculated as the sum of days of supply + a grace period of 14 days (in case of treatment discontinuation). A gap period of 30 days between the estimated end of supply and any following prescription of the index drug is allowed.

Since NOACs are prescribed in a fixed dose, the days of supply corresponds to the number of tablets in a dispensed package for rivaroxaban and edoxaban (used once daily) or half the number of tablets in a package for apixaban (used twice daily).

As of an international normalized ratio (INR) between 2 and 3, phenprocoumon patients are often asked to titrate or change their daily doses. Therefore, the exposure time calculation for phenprocoumon is not straightforward . In an anonymous empirical data collection using phenprocoumon diaries of anticoagulated NVAF patients in the university medical center of Schleswig-Holstein information on phenprocoumon dosing will be collected. The results of this survey will be used to calculate a median daily dose which will then be used as the basis for the phenprocoumon exposure time in this study.

As a sensitivity analysis, to account for the intra- and interpersonal variability of phenprocoumon treatment, a personalized defined daily dose (pDDD) based on the observed phenprocoumon prescriptions for each patient in the InGef database will be calculated. For this purpose, amount of active ingredient (AAI) dispensed to each patient of the phenprocoumon group will be obtained for each prescription. A prescribed personalized daily dose (pPDD) representing the average daily dose taken during follow-up will be computed for each patient i such that:

$$pPDD_{i} = \frac{\sum_{k=1}^{K-1} AAI_{i,k}}{T_{i}}$$

- $k = \text{index of the prescriptions received during follow-up } (k \in \{1, K\}).$

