9.3.3 Covariate definition

All demographic and clinical characteristics will be assessed based on primary and secondary hospital diagnoses and verified ambulatory diagnoses (ICD-10 GM codes), OPS codes, EBM codes and ATC codes as defined in Annex 3: Additional information. Unless otherwise mentioned, all information on covariates will be collected in the baseline period., i.e. in the 365 days prior to the index date). The assessment date for hospital diagnoses will be the admission date of the respective hospitalization and for ambulatory diagnoses the date of the first encounter with the diagnosing physician in the respective quarter (as ambulatory diagnoses are available on a quarterly basis only). Data derived from OPS codes and EBM codes will be assessed on the exact date.

Demographic characteristics

- Gender at index date
- Age at index date
- Age at index date categorized: 18–39, 40–44, 45–49, ..., 85-89, 90+ years

Clinical characteristics

- CHADS₂ score
- CHA₂DS₂-VASc score
- modified HAS-BLED score (the INR will not be included in the calculation of the score because this information is not available in the InGef database, end-stage renal disease will not be considered as these patients will be excluded from the analysis)
- Comorbidities
 - o Alcohol abuse
 - o Anemia
 - Aortic plaque
 - o Anemia
 - Coronary heart disease
 - Angina pectoris
 - Myocardial infarction
 - Acute ischemic heart diseases
 - Chronic ischemic heart disease
 - Coronary artery bypass graft(s)
 - Percutaneous coronary intervention
 - o Dementia
 - o Depression
 - o Diabetes mellitus
 - o Drug abuse
 - o Gastric or peptic ulcer disease/diseases of gastrointestinal tract
 - o Heart failure
 - History of major bleeding (hospitalization only)
 - o Hypertension
 - Hypothyroidism

- o Inflammatory bowel disease
- IS or transient ischemic attack
- Other cerebrovascular disease
- o Liver disease
- o Hyperlipidemia
- o Volume depletion
- Other metabolic disorders
- o Obesity
- Peripheral arterial disease
- o Psychosis
- o Pulmonary disease
- o Rheumatoid arthritis/collagen vascular disease
- Tobacco abuse
- o Other vascular disease
- Malignant cancer (except non-melanoma skin cancer)
- Comedications
 - o Angiotensin-converting enzyme inhibitors or angiotensin-receptor blockers
 - o Antiarrhythmics
 - o Antidepressants
 - o Antiplatelets
 - Antiulcer drugs (except proton-pump inhibitors)
 - o Calcium channel blockers
 - o Diabetes drugs
 - o Diuretics

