9.4 Data sources

This study will be conducted based on the InGef (former HRI) database which is an anonymized healthcare claims database covering all geographic regions of Germany. It includes longitudinal data from approx. 6.7 million Germans insured in one of approx. 64 German SHIs currently contributing data to the database (mainly company or guild health insurances).

Claims data are transferred directly from health care providers to a specialized data center owned by SHIs, which provides data warehouse and IT services. In the data center (acting as a trust center), data is anonymized before entering the InGef database. Data are anonymized with respect to individual insured members, health care providers (e.g. physicians, practices, hospitals, pharmacies), and the respective SHI. The most important data elements included in the database are displayed in Table 2. The time period covered by the database is limited to a look-back period of 6 years starting with the most current complete year of data (11).

Table 2 Information included	in the InGef Database
-------------------------------------	-----------------------

Demographics

Gender

Age

Date of death

	Region for place of living				
	Insurance status (e.g. retired, family insurance)				
	Date of insurance start and end (observation period)				
Outpatient Care	Diagnosis (ICD 10-GM Codes) and quarter in which the diagnosis was documented				
	Procedures performed (e.g. laboratory, radiology, echocardiography) (EBM-Codes) and day of performance				
	Type of specialist that documented the diagnosis and performed the procedure (e.g. cardiologist, general practitioner)				
	Costs of outpatient care				
Pharmacy	Drug dispensed by central pharmaceutical number (package level) – this is mapped to ATC codes and DDD's by InGef				
	Quantity dispensed				
	Day of prescription				
	Day of dispensing				
	Type of doctor prescribing (e.g. cardiologist, general practitioner)				
	Costs of drugs dispensed from SHI perspective (without individual rebates between single sickness funds and pharmaceutical companies)				
Hospital care	Main diagnosis (ICD 10-GM Codes) and additional diagnoses				
	Performed procedures and surgeries (e.g. pacemaker implant, implantable cardioverter defibrillator				
	Date of hospital admission				
	Reason for admission (e.g. accident, emergency, normal)				
	Date of end of hospital stay				
	Reason of end of hospital stay (e.g. death in hospital, normal end)				

	DRG-Code			

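### The VTE exclusion in 9.2.3 runs to the end of the index quarter, so a dated hospital VTE admission after treatment start removes the patient and any outcome event

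*Protocol*

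**What the plan says.** Section 9.2.3 of the protocol excludes patients with a verified ambulatory or a primary or secondary hospital discharge "diagnosis of venous thromboembolism (VTE) in the previous or same quarter of the index date". It sets no limit at the index date. Annex 3 lists the VTE codes (I26, I80, I81, I82.2, I82.9) and adds no date condition.

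The neighbouring exclusions are worded differently. One reads "A claim for hip or knee replacement surgery in the 60 days prior to or on the index date"; another removes patients with a "diagnosis of end-stage kidney disease or a claim for dialysis in the baseline period". The rest of the list likewise refers to the baseline period, to 60 days up to and including the index date, or to the index prescription itself.

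Time zero is clear: "patients will be followed from the index date until the first diagnosis of the respective outcome event" (9.2.3), and "Exposure time for phenprocoumon and NOACs starts on the index date" (9.3.1).

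On dating, 9.3.3 states for covariates that "The assessment date for hospital diagnoses will be the admission date of the respective hospitalization", whereas "ambulatory diagnoses are available on a quarterly basis only". Table 2 in 9.4 lists "Date of hospital admission" among the available data elements.

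**The concern.** A cohort that starts at first dispensing should decide eligibility from what is known on that day. Under this rule, the rest of the index quarter is on-treatment time that also decides who belongs to the cohort.

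Take a patient dispensed the index drug on 5 January, admitted with ischemic stroke on 1 February and with pulmonary embolism on 20 March. Follow-up for IS/SE would have ended with the stroke. The later embolism nevertheless removes the patient and the stroke from the analysis.

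The rule can also act on the outcome admission itself. IS, SE and ICH are taken from the primary discharge diagnosis (9.3.2), while the VTE exclusion also counts secondary diagnoses. A stroke or ICH stay in the index quarter with a secondary VTE code both creates the event and deletes it.

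At stake is selection on post-baseline information in the comparisons with phenprocoumon. The length of the look-ahead also depends on an irrelevant fact, the day of the quarter on which treatment began.

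**Working it through.** The plan states no figure for this window, so there is none to reproduce. The check has two parts: the wording, and the scale.

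**Wording**

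1. The window is the previous calendar quarter plus the whole quarter containing the index date (9.2.3).
2. Follow-up and exposure start on the index date (9.2.3, 9.3.1). Days after it in the same quarter are therefore follow-up time.
3. Quarterly recording explains a same-quarter rule for ambulatory codes only. For hospital codes the admission date is in the database (Table 2), and 9.3.3 already uses it to date hospital diagnoses.
4. Heparin or fondaparinux gives a contrast within 9.2.3. A prescription in the 60 days up to the index date excludes the patient; a later one only censors. A later hospital VTE within the quarter removes all person-time from day one.

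**Length of the look-ahead**

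Assume index dates spread evenly over the enrollment period, 1 January 2013 to 30 June 2017. Averaging the days from each date to the end of its calendar quarter gives a mean of 45.1 days. The minimum is 0 (last day of a quarter) and the maximum 91 (first day of a 92-day quarter).

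**Patients affected**

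Expected starters from 9.5: 35,400 + 16,800 + 30,200 + 1,600 = 84,000 in the four study groups. The VTE rate on treatment is not in the documents; 0.3 to 1.0 per 100 person-years is assumed.

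Formula: starters × rate × mean look-ahead / 365.25.

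- Low: 84,000 × 0.003 × 45.1 / 365.25 = 31.1
- High: 84,000 × 0.010 × 45.1 / 365.25 = 103.7

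That is about 31 to 104 patients, or 0.04% to 0.12%. Taking half a quarter (365 / 8 = 45.6 days) and a 365-day year moves the upper figure to 105. A wider assumed range of 0.2 to 2 per 100 person-years gives about 21 to 207. All these counts include VTE seen only in ambulatory care, so hospital VTE alone accounts for fewer.

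**Outcome events carried by these patients**

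Table 3 expects 885 + 454 + 664 + 35 = 2,038 IS/SE and 248 + 67 + 151 + 6 = 472 ICH events, assuming one year of follow-up per patient.

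| | Low (31.1 patients) | High (103.7 patients) |
|---|---|---|
| IS/SE at average risk (× 2,038 / 84,000) | 0.8 | 2.5 |
| ICH at average risk (× 472 / 84,000) | 0.2 | 0.6 |
| IS/SE at five times the risk (assumed) | 3.8 | 12.6 |
| ICH at five times the risk (assumed) | 0.9 | 2.9 |

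Even the largest entries are about 0.6% of the expected events (12.6 / 2,038 and 2.9 / 472). The table does not capture outcome stays with a secondary VTE code. There the removed patient has an event for certain, and the documents give no frequency.

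**Edoxaban**

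Removed: 1,600 × 0.003 × 45.1 / 365.25 = 0.6, up to 1,600 × 0.010 × 45.1 / 365.25 = 2.0 patients. At the Table 3 ICH rate of 0.004, that is 0.002 to 0.008 events, or 0.01 to 0.04 at five times the risk.

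**The case against.** The best defence is that the window serves specificity of indication. The study drugs may also be started for VTE, and a code that appears shortly after dispensing can reveal that the prescription was not for atrial fibrillation. This stands for ambulatory codes, which carry no exact day. It is weak for hospital codes: an admission that prompted the prescription would normally precede dispensing.

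It can also be said that VTE is not the only exclusion exposed to look-ahead. If the first-encounter date in 9.3.3 is applied to eligibility, an ambulatory code entered later in the index quarter could count as baseline for valvular atrial fibrillation or end-stage kidney disease too. That is correct. The contrast with the other exclusions therefore lies in how they are worded, and the point is confined to hospital VTE. For the same reason, closing the hospital window does not make eligibility depend on pre-index information alone. A patient with a later hospital VTE stays excluded if an ambulatory VTE code is entered in the same quarter.

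Finally, the effect is small. The figures above bear this out.

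Two stronger readings are tempting. A reader might infer that the rule favours the drug that protects less well, by removing its treatment failures. The documents give no VTE rate by drug and no link between VTE and IS/SE or ICH, so no direction follows. A reader might also infer that the edoxaban ICH analysis, with 6 expected events, is vulnerable to one lost patient. That patient would have to be an ICH case, and the expected number of such losses is well under 0.1.

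**Conclusion.** The point holds for hospital diagnoses. As worded, 9.2.3 lets a hospital VTE after treatment start decide cohort membership and delete outcome events already observed, although the admission date needed to avoid this is available.

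The number affected is probably small: at most about 31 to 104 of 84,000 starters, and fewer for hospital VTE alone. This rests on an assumed rate of 0.3 to 1.0 VTE per 100 person-years, evenly spread index dates and the expected group sizes in 9.5. A hazard ratio is biased only if the removals differ between drugs in a way related to the outcome, which the documents neither show nor rule out. The change is worth making because it is a cheap correction of a time-zero fault, without any claim that the results would move materially.

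**What to change.** In 9.2.3, count a hospital VTE diagnosis as an exclusion only if its admission date is on or before the index date. Keep the present start of the look-back, the beginning of the previous quarter. Keep ambulatory VTE codes of the previous and the index quarter, since they are recorded by quarter. Add one sensitivity analysis that ignores ambulatory VTE codes of the index quarter, to show how much the remaining look-ahead matters.

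The cost is one sentence, one date condition in the programming and one extra run. The downside is that a few patients treated for VTE whose hospital admission follows dispensing will stay in the cohort.

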- T= number of days between the first and the last prescription during follow-up

For the sake of simplicity, only prescriptions of patients who were solely treated with phenprocoumon during follow-up will be included in the computation of the empirical DDD (eDDD). Patients with a pDDD below the 5th or above the 95th percentile and patients with only one prescription for phenprocoumon will be assigned the median pDDD (=eDDD) over all patients.

The exposure time (ET) corrected from the intra- and interpersonal variability of phenprocoumon treatments can be computed for each patient i as:

$$ET_i = \frac{\sum_{k=1}^{K} AAI_{i,k}}{pDDD}$$

Patients will be considered as having discontinued treatment with the index drug, if they did not receive a subsequent prescription of the respective drug between the last prescription and a gap period of 30 days.

Patients will be considered as having switched from the index drug to phenprocoumon or another NOAC if they received a prescription of the respective drug during continuous exposure time to the index drug as described above. The date of the first prescription of phenprocoumon or another

NOAC will be defined as the date of treatment switch at which patients will be censored. For the comparison of the effectiveness outcomes in patients receiving reduced vs. standard doses of NOACs (other objectives), patients will also be censored if they switch from reduced to standard dose or vice versa.

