9.7.2 Main analysis

Analyses will be conducted in line with good statistical practices. Models will use confounding factors to adjust for group differences. However, unmeasured confounding and resulting confounding bias affecting point estimates, confidence intervals and any p-values in the treatment group comparisons may remain.

In a first step, Cox proportional hazards regression models will be applied in in each treatment group compared to phenprocoumon (reference) to estimate crude and confounder adjusted hazard ratios (HRs) of the above mentioned outcomes as well as treatment discontinuation (persistence) with accompanying 95% confidence intervals and *p*-values. Persistence (risk of non-persistence) will also be calculated separately for specific time points of interest (months 3, 6, 9, 12, 18 and 24). In the analysis of reduced vs. standard dose of NOACs, the standard dose will be used as reference. Kaplan-Meier cumulative incidence plots will be generated to characterize risk of outcome events of interest over time.

Information on confounding factors which are planned to be included in the models as well as in the estimation of the propensity score can be found in section 9.3.3.

In a second step, we will use the stabilized inverse probability of treatment weighting (IPTW) approach based on the propensity score to adjust for potential confounding resulting from imbalances in the baseline characteristics of different treatment groups. The objective of IPTW

based analysis is to create a weighted sample, for which the distribution of possible confounding variables is approximately the same between comparison groups (12,13). The propensity score is defined as the patient's probability to receive a treatment under investigation (i.e. phenprocoumon for main analyses and standard dose for the analyses of reduced vs. standard dose of NOACs) given a set of known patient's baseline characteristics. Propensity scores will be calculated using multiple logistic regression on a relevant set of patient characteristics listed in section 9.3.1 for each 1:1 comparison separately, e.g. rivaroxaban vs. phenprocoumon, rivaroxaban 15 mg vs. rivaroxaban 20 mg etc.

Let Z be an indicator variable relating to the treatment received by a patient, Z = 1 for an active treatment (e.g. rivaroxaban), Z = 0 for a control treatment (warfarin), and let X denote a vector of observed patient baseline characteristics. Then the propensity score is e = P(Z = 1|X). The inverse

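### Persistence is analysed with switchers censored, so reported non-persistence cannot reflect switching; separately, the 30-day gap has two start dates

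*Protocol*

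**What the plan says.** **Switching.** Protocol 8.2 lists treatment persistence as a secondary objective. Section 9.7.2 analyses it by Cox regression under the label "treatment discontinuation (persistence" and adds: "Persistence (risk of non-persistence) will also be calculated separately for specific time points of interest", namely months 3, 6, 9, 12, 18 and 24. Section 9.2.3 sets the end of follow-up: "Patients will be censored in all analyses if they switch to phenprocoumon or another NOAC (including dabigatran". The same sentence lists a warfarin prescription as a further, separate reason for censoring. The only opening for an exception is "For specific analyses, the end of follow-up may differ as described in 9.3.1".

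Section 9.3.1 does not use that opening for persistence. It defines a switch as another drug dispensed to patients "if they received a prescription of the respective drug during continuous exposure time to the index drug" and repeats the rule: the first prescription of phenprocoumon or another "NOAC will be defined as the date of treatment switch at which patients will be censored". Its only addition is censoring at a change of dose in the reduced versus standard dose comparison. Section 9.3.3 lists switch and discontinuation as different types of cohort exit.

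**Gap.** Section 9.3.1 first says: "A gap period of 30 days between the estimated end of supply and any following prescription of the index drug is allowed". Later it defines patients as having discontinued "if they did not receive a subsequent prescription of the respective drug between the last prescription and a gap period of 30 days".

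**The concern.** Someone who moves to another anticoagulant has left the index drug. Once they stop filling it, they would meet the discontinuation rule, but they are censored before that can happen. The month 3 to 24 risks then describe a setting in which nobody switches, and the hazard ratio ignores any difference in switching between a NOAC and phenprocoumon. Two drugs with the same rate of plain stopping would look equally persistent even if patients switched away from one far more often.

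The gap wording raises a different matter. Discontinuation is the event in the persistence analysis, and it also ends follow-up for the as-treated outcomes, which include the primary ones. A rule with two possible start dates can be programmed in two ways.

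**Working it through.** The protocol states no figure for persistence, discontinuation or switching, so there is none to reproduce.

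**Part 1: effect of censoring switchers.** Assumptions: constant and independent hazards, *d* for discontinuation and *s* for a switch during exposure; *d* = 0.2 to 0.5 and *s* = 0.05 to 0.20 per year, chosen for illustration. The protocol names no estimator for the time-point risks. I take 1 − Kaplan-Meier, in line with the Kaplan-Meier plots in 9.7.2.

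- Reported risk, switchers censored: 1 − exp(−*d·t*). It does not contain *s*.
- Share who left the index drug for either reason: 1 − exp(−(*d* + *s*)*t*).
- Cumulative incidence of stopping without switching: *d*/(*d* + *s*) × [1 − exp(−(*d* + *s*)*t*)].

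With *d* = 0.30 per year:

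| *s* per year | Reported, 12 mo | Left index drug, 12 mo | Stopped without switching, 12 mo | Reported, 24 mo | Left index drug, 24 mo |
|---|---|---|---|---|---|
| 0.05 | 25.9% | 29.5% | 25.3% | 45.1% | 50.3% |
| 0.10 | 25.9% | 33.0% | 24.7% | 45.1% | 55.1% |
| 0.20 | 25.9% | 39.3% | 23.6% | 45.1% | 63.2% |

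For example, at *s* = 0.10 and 12 months: 1 − exp(−0.30) = 25.9%; 1 − exp(−0.40) = 33.0%; 0.30/0.40 × 33.0% = 24.7%.

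Over the whole assumed range, the 12-month shortfall against the share who left the drug runs from 42.3 − 39.3 = 3.0 points (*d* = 0.5, *s* = 0.05) to 33.0 − 18.1 = 14.9 points (*d* = 0.2, *s* = 0.20).

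Hazard ratio: with switchers censored it is *d*₁/*d*₀; with switches counted it is (*d*₁ + *s*₁)/(*d*₀ + *s*₀). With *d* = 0.30 on both drugs and switching at 0.05 versus 0.20, the first is 0.30/0.30 = 1.00 and the second 0.35/0.50 = 0.70, or 0.50/0.35 = 1.43 with the roles reversed.

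**Part 2: the gap.** Annex 3 lists an apixaban 5 mg pack labelled 5x20, which I read as 100 tablets. Section 9.3.1 gives half the tablet count as days of supply, so 50 days. The last refill day that avoids discontinuation is:

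- counted from the end of supply: 50 + 30 = day 80;
- counted literally from the last prescription: day 30.

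Under the second count, a fully adherent patient refilling on day 50 has already discontinued. The same happens with any pack lasting more than 30 days that is refilled only as it runs out. This raises non-persistence according to pack size, and switching plays no part in it.

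**The case against.** **Censoring may be a deliberate choice of outcome.** Section 9.7.2 equates persistence with discontinuation, and 9.3.1 keeps discontinuation and switching apart. A Cox model with switchers censored is a standard cause-specific hazard model for discontinuation, and 9.3.3 records switching as a type of exit. This stands for the hazard ratio, if that is the intended target. It does not rescue the time-point risks: for stopping without switching, switching is a competing event, and 1 − Kaplan-Meier slightly overstates the risk (25.9% against 24.7% above).

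**Not every switch is lost.** Only switches during continuous exposure are censored. Someone who starts another drug after exposure has ended already counts as discontinued. This stands and limits the shortfall.

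**The gap conflict may be loose wording.** The first sentence defines the gap and the second reuses the term. The literal second reading would make the days-of-supply calculation pointless for longer packs and would clash with the stockpiling analysis in 9.7.3, which relies on the end of supply. This stands as to intent: the end of supply is clearly meant. The text still conflicts in the rule that ends follow-up.

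**Weight.** Persistence is one of many secondary objectives, and the Abstract says that p-values and intervals must not be read as confirmatory. This limits the severity, but the month 3 to 24 figures will still be read as they stand.

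**Conclusion.** Both defects hold, as two separate points.

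1. With switchers censored, the persistence results cannot respond to switching. The time-point risks give neither the share who left the index drug (too low) nor the cumulative incidence of stopping without switching (slightly too high). The first direction needs no assumed rate, only that some switching occurs during exposure. The size does: about 3 to 15 points at 12 months over the assumed range.
2. The 30-day gap has two start dates in 9.3.1. If programmed literally from the last prescription, adherent users of longer packs would be called discontinued and their as-treated follow-up would end early.

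Three stronger readings are not supported. A reader might infer that the two defects together understate non-persistence; the literal gap rule pushes the other way. A reader might infer that a particular drug, such as phenprocoumon, is flattered; without switch rates in the protocol, neither the drug nor the amount can be named. A reader might infer that the primary results will be distorted by the gap rule; that happens only if the less plausible reading is programmed.

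**What to change.** **Persistence.** In 9.2.3 and 9.3.1, exempt the persistence analysis from censoring at a move to another oral anticoagulant. Name dabigatran and warfarin explicitly: 9.2.3 lists warfarin apart from switching, so an exemption for switches alone would still censor those patients. Define non-persistence as the first of gap-defined discontinuation or switch, and report the two components as competing events with cumulative incidence at the stated months.

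**Gap.** Reword the discontinuation definition in 9.3.1 so that the 30 days run from the end of supply, as in the earlier sentence of that section and as the days-of-supply and stockpiling rules already require.

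**Cost.** A few sentences in two sections, plus one cumulative-incidence output for a secondary objective. The dates of switch and of warfarin prescriptions are already needed for censoring, so no new data are required.
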